3.2 DISCUSSION OF TRIAL DESIGN, INCLUDING THE CHOICE OF CONTROL GROUP

A 3-week treatment period is justified because the pharmacokinetic results obtained in healthy volunteers suggested that pharmacokinetic steady state is reached within 3 weeks.

Patients with moderate to severe COPD will be included in this trial. Pharmacotherapy with long-acting bronchodilators (as single-agent therapy or as combination therapy) is the recommended maintenance treatment for these patients according to various international clinical guidelines for the management of this disease [[P01-02794](#), [P04-07409](#)]. Therefore, the systemic exposure in Chinese patients with COPD under maintenance treatment, *i.e.* at pharmacokinetic steady state, is the relevant endpoint for determining the PK of tiotropium and olodaterol in the dose combination to be used in the FDC.

Following once daily inhalation of the tiotropium + olodaterol FDC, the terminal half-life of both tiotropium and olodaterol was about 60 h and pharmacokinetic steady state was reached latest at day 8 to 10 for both compounds [[U08-2169](#)]

3.3 SELECTION OF TRIAL POPULATION

A log of all patients enrolled into the trial (i.e. who have signed informed consent) will be maintained in the ISF at the investigational site irrespective of whether they have been treated with investigational drug or not.

3.3.1 Main diagnosis for trial entry

16 patients will be included in the trial to ensure that a minimum of 12 evaluable patients of both sex, 40 years of age or older, and with a diagnosis of COPD complete the study, trial could be ended in case 12 evaluable patients are available. The evaluable patients are defined as the patients who have available blood samples for PK measurement at Visit 2, 3 and 4 as described in Flowchart. Every effort should be made to keep patients in the study until they complete all study procedures and all test days.

Please refer to [section 8.3.1](#) (Source Documents) for the documentation requirements pertaining to the in- and exclusion criteria.

3.3.2 Inclusion criteria

1. All patients must sign an informed consent consistent with ICH-GCP guidelines and local legislations prior to any study-related procedures, which includes medication washout and restrictions.
2. All patients must have a diagnosis of COPD [[P11-05865](#)] and must meet the following spirometric criteria:

Patients must have relatively stable airway obstruction with a post-bronchodilator FEV₁ ≥30% of predicted normal and <80% of predicted normal (ECSC, [[R94-1408](#)]); and a post-bronchodilator FEV₁/ FVC <70% at Visit 1 (See [Appendix 10.4](#) for ECSC predicted normal equations).

3. Male or female patients, 40 years of age or older.
4. Patients must be current or ex-smokers with a smoking history of more than 10 pack years. (See [Appendix 10.4](#) for calculation).

Patients who have never smoked cigarettes must be excluded.

5. Patients must be able to
 - perform technically acceptable pulmonary function tests,
 - maintain medication worksheet records during the study period,
 - perform all other assessments as required in the protocol.
6. Patients must be able to inhale medication in a competent manner from the RESPIMAT inhaler (See [Appendix 10.2](#)) and from a metered dose inhaler (MDI).
7. Male or female patients. Women of childbearing potential* must be ready and able to use highly effective methods of birth control per ICH M3(R2) that result in a low failure rate of less than 1% per year when used consistently and correctly. A list of contraception methods meeting these criteria is provided in the patient information.

*Women of childbearing potential are defined as:

Any female who has experienced menarche and does not meet the criteria for "women not of childbearing potential" as described below.

Women not of childbearing potential are defined as:

Women who are postmenopausal (12 months with no menses without an alternative medical cause) or who are permanently sterilized (e.g., tubal occlusion, hysterectomy, bilateral oophorectomy or bilateral salpingectomy).

3.3.3 Exclusion criteria

1. Patients with a significant disease other than COPD; a significant disease is defined as a disease which, in the opinion of the investigator, may (i) put the patient at risk because of participation in the study, (ii) influence the results of the study, or (iii) cause concern regarding the patient's ability to participate in the study.
2. Patients with a, in the opinion of the investigator, clinically relevant abnormal baseline haematology, blood chemistry, or urinalysis; all patients with an SGOT > 2 x ULN, SGPT > 2 x ULN, bilirubin > 2 x ULN or creatinine > 2 x ULN will be excluded regardless of clinical condition (a repeat laboratory evaluation will not be conducted in these patients).
3. Patients with a history of asthma. For patients with allergic rhinitis or atopy, source documentation is required to verify that the patient does not have asthma. If a patient has a total blood eosinophil count $\geq 600/\text{mm}^3$, source documentation is required to verify that the increased eosinophil count is related to a non-asthmatic condition.

Patients with any of the following conditions:

4. A diagnosis of thyrotoxicosis (due to the known class side effect profile of β_2 -agonists).
5. A diagnosis of paroxysmal tachycardia (>100 beats per minute) (due to the known class side effect profile of β_2 -agonists)
6. A history of myocardial infarction within 1 year of screening visit (Visit 1).
7. Unstable or life-threatening cardiac arrhythmia.
8. Hospitalization for heart failure within the past year.
9. Known active tuberculosis.
10. A malignancy for which patient has undergone resection, radiation therapy or chemotherapy within last five years (patients with treated basal cell carcinoma are allowed).
11. A history of life-threatening pulmonary obstruction.
12. A history of cystic fibrosis.
13. Clinically evident bronchiectasis.
14. A history of significant alcohol or drug abuse.
15. Patients who have undergone thoracotomy with pulmonary resection (patients with a history of thoracotomy for other reasons should be evaluated as per exclusion criterion No. 1).
16. Patients being treated with oral or patch β -adrenergics.
17. Patients being treated with oral corticosteroid medication at unstable doses (i.e., less than six weeks on a stable dose) or at doses in excess of the equivalent of 10 mg of prednisone per day or 20 mg every other day.
18. Patients who regularly use daytime oxygen therapy for more than one hour per day and in the investigator's opinion will be unable to abstain from the use of oxygen therapy during clinic visits.
19. Patients who have completed a pulmonary rehabilitation program in the six weeks prior to the screening visit (Visit 1) or patients who are currently in a pulmonary rehabilitation program.

20. Patients who have taken an investigational drug within one month or six half lives or (in case the investigational drug (sub) class is listed in [Table 4.2.2.1:1](#)) within the wash out period specified in Table 4.2.2.1:1 (whichever is greater) prior to screening visit (Visit 1).
21. Patients with known hypersensitivity to β -adrenergics and/or anticholinergic drugs, BAC, EDTA or any other component of the RESPIMAT inhalation solution.
22. Women who are pregnant, nursing, or who plan to become pregnant while in the trial
23. Women of childbearing potential not using two highly effective methods of birth control*. Female patients will be considered to be of childbearing potential unless surgically sterilised by hysterectomy or bilateral tubal ligation, or post-menopausal for at least two years.
 - * as per ICH M3 (R2) [[R10-5669](#)]: a highly effective method of birth control is defined as those which result in a low failure rate (i.e., less than 1% per year) when used consistently and correctly.
24. Patients who have previously been allocated in this study or are currently participating in another study.
25. Patients who are unable to comply with pulmonary medication restrictions prior to allocation.

Note:

1. Extreme caution should be used when including patients:
 - with cardiovascular disorders, especially coronary insufficiency and hypertension*
 - being treated with monoamine oxidase inhibitors or tricyclic antidepressants*
2. Caution should be used when including patients on treatment with non potassium-sparing diuretics*
3. Patients with moderate to severe renal impairment (creatinine clearance ≤ 50 mL/min) should be monitored closely by the investigator, as tiotropium is a predominantly renally excreted drug.
4. Beta-blockers do not only block the pulmonary effect of beta-agonists, but may also produce severe bronchospasm in patients with COPD. Therefore, patients should not normally be treated with beta-blockers. However, under certain circumstances, e.g., as prophylaxis after myocardial infarction, there may be no acceptable alternatives to the use of beta-adrenergic blocking agents in patients with COPD. In this setting, cardio selective beta-blockers could be considered, although they should be administered with caution.*
5. As an anticholinergic drug, tiotropium may potentially worsen symptoms and signs associated with narrow-angle glaucoma, prostatic hyperplasia or bladder-neck obstruction and should be used with caution in patients with any of these conditions.

* cf prescribing information for registered LABAs (salmeterol/formoterol) and olodaterol

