Safety will be monitored (as described in [section 5.2](#)) at site visits and withdrawal criteria is provided for investigators' consideration (as listed in [section 3.3.4.1](#)). Women of childbearing potential may be included in clinical trials for tiotropium + olodaterol provided appropriate precautions are taken to minimize the risk of pregnancy. These precautions include pregnancy testing and use of a highly effective method of birth control. Continued testing and monitoring during the trial should be sufficient to ensure compliance with the measures not to become pregnant during the period of drug exposure (including the 3 weeks follow-up period) [[R10-5669](#)].

[figure not shown]
Safety will be monitored including adverse events, physical examination, vital signs, laboratory tests, pregnancy tests, , 12-lead ECG (as described in Section 5.2) at site visits.

Potential benefits for participating patients in this trial are associated with the bronchodilating effects of the active treatments during the treatment period. Careful monitoring of safety is planned at site to decrease risks. This trial is designed to provide data for evaluating the pharmacokinetic characteristics of tiotropium + olodaterol FDC at the planned registration dose in Chinese patients with COPD. The potential benefits for patients outweigh potential risks.

Although rare, a potential for drug-induced liver injury is under constant surveillance by sponsors and regulators. Therefore, this trial requires timely detection, evaluation, and follow-up of laboratory alterations in selected liver laboratory parameters to ensure patients' safety, see also [section 5.3.6.1](#).

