### **6.2 IMPORTANT PROTOCOL VIOLATIONS**

[Table 6.2: 1](#) gives the important protocol violations (PVs) for this trial. Patients with important PVs relevant to the evaluation of PK will be excluded from PK analysis. If data shows other important PVs, this table will be supplemented accordingly at the Database lock (DBL) meeting at latest.

Table 6.2: 1 Important protocol violations

Category / Code	Description	Comment/Example	Excluded from
A	Entrance criteria not met		
A1	Respiratory conditions		
A1.1	Without diagnosis of COPD	IN 2 not met Detected manually	None
A1.2	Age<40	IN 3 not met Detected manually	None
A1.3	Never smoke or ex-smokers with a smoking history of less than 10 packs year	IN 4 not met Detected automatically	None
A1.4	Patients are not capable to enter the trial	IN 5 not met Detected manually	None
A1.5	Patients are unable to inhale medication	IN 6 not met Detected manually	None
A1.6	Women of childbearing potential but are unable to use effective methods in birth control	IN 7 not met or EX 23 met Detected manually	None
A2	Exclusion criteria met		
A2.1	With significant disease other than COPD	EX1 Detected manually	None
A2.2	With clinically relevant abnormal baseline haematology, blood chemistry, or urinalysis	EX2 Detected manually Detected automatically for SGOT, SGPT, bilirubin, creatinine	None
A2.3	With asthma	EX3 Detected manually	None
A2.4	Patients are under conditions specified in exclusion criteria 4-14	EX4-14 Detected manually	None
A2.5	Have undergone thoracotomy with pulmonary resection	EX15 Detected manually	None
A2.6	Treated with any oral $\beta$ -adrenergics	EX16 Detected manually	None
A2.7	Treated with oral corticosteroid medication at unstable dose	EX17 Detected manually	None
A2.8	Regularly use daytime oxygen therapy	EX18 Detected manually	None
A2.9	Completed a pulmonary rehabilitation program in the six weeks prior to visit 1 or currently in the program	EX19 Detected manually	None
A2.10	Insufficient wash-out period	EX20 Detected manually	None

Category / Code	Description	Comment/Example	Excluded from
A2.11	Hypersensitivity to $\beta$ -adrenergics and/or anticholinergic drugs, BAC, EDTA or any other component of the RESPIMAT inhalation solution	EX21 Detected manually	None
A2.12	Pregnant or nursing women	EX22 Detected manually	None
A2.13	Patients who were in this study or are currently participating another study	EX24 Detected manually	None

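### Inclusion criterion 7 and exclusion criterion 23 define childbearing potential differently, and the pregnancy-test instructions do not say which definition applies

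*Protocol*

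**What the plan says.** Protocol section 3.3.2, inclusion criterion 7, defines who is not of childbearing potential: "Women who are postmenopausal (12 months with no menses without an alternative medical cause) or who are permanently sterilized". Its sterilisation examples form an open list that includes bilateral oophorectomy and bilateral salpingectomy. Women who are of childbearing potential "must be ready and able to use highly effective methods of birth control per ICH M3(R2"), and no number of methods is given.

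Section 3.3.3, exclusion criterion 23, bars "Women of childbearing potential not using two highly effective methods of birth control". It then gives its own definition: a woman counts as of childbearing potential "unless surgically sterilised by hysterectomy or bilateral tubal ligation, or post-menopausal for at least two years". This list is closed. Neither criterion refers to the other.

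Section 2.3, in the benefit-risk discussion, uses the singular: "These precautions include pregnancy testing and use of a highly effective method of birth control".

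Flow-chart footnote 4 and section 5.3.3 require a serum HCG test at Visit 1 and urine tests at Visits 2, 4 and 5 in women of childbearing potential. Neither place says which definition is meant.

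SAP Table 6.2:1, code A1.6, describes the violation as "Women of childbearing potential but are unable to use effective methods in birth control". It is triggered when inclusion 7 is not met or exclusion 23 is met, is detected manually, and leads to exclusion from no analysis set.

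**The concern.** Two definitions of the same term are in force, each written as the rule. The term does two jobs. It decides which women must meet the contraception requirement, and it decides who is tested for pregnancy at screening, before dosing and at follow-up. Section 2.3 justifies admitting women of childbearing potential by pregnancy testing, contraception and continued monitoring, and that safeguard needs one agreed population. If sites can read the population in two ways, a woman may be enrolled who should not have been, or a test may be omitted that the other definition calls for.

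**Working it through.** No sample size, power or error rate is involved, so the check is a comparison of texts.

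**The wording side by side**

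| Item | Inclusion 7 | Exclusion 23 | Section 2.3 |
|---|---|---|---|
| Menopause | 12 months | at least two years | not stated |
| Sterilisation | tubal occlusion, hysterectomy, bilateral oophorectomy, bilateral salpingectomy (open list) | hysterectomy, bilateral tubal ligation (closed list) | not stated |
| Contraception | highly effective methods, no number | two | one |

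**Classification by status**

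Eight reproductive statuses were put through both definitions. Those after oophorectomy or salpingectomy are taken to be not yet two years post-menopausal.

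| Status | Childbearing potential, inclusion 7 | Childbearing potential, exclusion 23 |
|---|---|---|
| Premenopausal | yes | yes |
| Post-menopausal under 12 months | yes | yes |
| Post-menopausal 12 to under 24 months | no | **yes** |
| Post-menopausal 24 months or more | no | no |
| Tubal ligation | no | no |
| Hysterectomy | no | no |
| Bilateral oophorectomy | no | **yes** |
| Bilateral salpingectomy | no | **yes** |

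The definitions disagree in 3 of 8 statuses. None of these 3 depends on how the contraception wording is read.

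**Adding the number of methods in use (0, 1 or 2)**

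This gives 8 × 3 = 24 combinations. Inclusion 7 is taken as met if the woman is not of childbearing potential by its definition or uses at least one method. Exclusion 23 is taken as met (she is barred) if she is of childbearing potential by its definition and uses fewer than two.

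- In the 3 disputed statuses with 0 or 1 method, she passes inclusion 7 and is barred by exclusion 23: 3 × 2 = 6 combinations.
- In the 2 statuses where both definitions say yes, exactly one method passes inclusion 7 and fails exclusion 23: 2 × 1 = 2 combinations. These two depend on reading the unnumbered plural in inclusion 7 as satisfied by one method.
- Total: 6 + 2 = 8 of 24. All run the same way: inclusion 7 is met and exclusion 23 bars her.

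**Pregnancy testing**

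In the 3 disputed statuses the test requirement depends on the definition used. If exclusion 23 is applied correctly, only women in these statuses who use two highly effective methods enter the trial: 3 × 1 = 3 of the 24 combinations. If a site works from inclusion 7 alone, women in these statuses using 0 or 1 method could also be enrolled, and by that same definition would not be tested.

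These counts show where the texts diverge. They are not frequencies, because the combinations are not equally common among patients.

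**Amendment log**

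Neither global amendment in section 11 addresses the two definitions.

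**The case against.** The strongest reply is that a patient must meet every inclusion criterion and no exclusion criterion. Exclusion 23 is the stricter text wherever the two differ, so it decides enrolment, and SAP code A1.6 combines the criteria in the same way. This stands. A reader might infer that a woman 18 months post-menopausal has a contradictory eligibility result. The documents do not support that: unless she uses two highly effective methods, she is barred.

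Second, correctly enrolled women in the disputed statuses would already be using two highly effective methods, a group likely to be close to empty here. This also stands and limits the size of the testing gap. It does not close the gap, because the rule that the criteria apply together says who enters, not who is tested.

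Third, an unnumbered plural is compatible with two methods, and section 2.3 is narrative rather than an eligibility rule. It would therefore go too far to count every fertile woman using one method as an established contradiction. The wording is uneven and worth aligning, but the point rests on menopause duration and sterilisation procedures.

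Two further inferences also fail. Not every woman after oophorectomy or salpingectomy is affected: one at least two years post-menopausal is exempt under both texts. And Amendment 2 does not show that screening out a few women harms recruitment. Its remark concerned a minimum of one third of each sex, which it deleted, so no such target remains.

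**Conclusion.** The conflict of definitions is real and stands in the current protocol. It has two consequences. A site relying on inclusion 7 could enrol a woman whom exclusion 23 bars, producing an important protocol violation under A1.6. And pregnancy testing is undetermined for women 12 to under 24 months post-menopausal, and for women after bilateral oophorectomy or salpingectomy who are not yet two years post-menopausal.

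The number affected is likely very small: 16 patients are planned, all aged 40 or older, and the sponsor expected few women. The documents give no figures on reproductive status, so this is a judgement and not an estimate. No PK endpoint, sample-size figure or analysis set changes. The point is worth correcting because it touches a safety check and the correction is one of wording.

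The conclusion assumes that the pregnancy-test instructions mean one of the two stated definitions, and that the patient information, which is not available here, does not settle the matter. Which definition or contraception requirement is right is not judged.

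**What to change.** Reconcile inclusion 7, exclusion 23 and section 2.3 to one definition of childbearing potential and one contraception requirement, both chosen by the sponsor. State them once, and refer to that statement from flow-chart footnote 4 and section 5.3.3 so that the tested population is explicit. Check that the patient information agrees. SAP code A1.6 needs no separate change to its trigger, because it cites the two criteria by number and follows any correction to them. The cost is protocol wording and any matching patient-information text. No new type of procedure, data item or analysis is needed.

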3.3.4 Removal of patients from therapy or assessments

3.3.4.1 Removal of individual patients

An individual patient is to be withdrawn from the trial if any of the following criteria apply:

1. The patient withdraws consent, without the need to justify the decision.
2. The patient is no longer able to participate for medical reasons (e.g. pregnancy, surgery, adverse events, or other diseases), or contraindications for exercise testing have occurred.

3. Administrative reasons (protocol violations, persistent non-compliance).
4. Decision by Boehringer Ingelheim to discontinue one or all patients (e.g., new toxicological findings or SAEs invalidate the earlier positive benefit–risk assessment).

No patient should be discontinued from the trial for a protocol violation before discussion with the clinical monitor. In the event of a COPD exacerbation, please contact the CML / TCM to discuss the possibilities to re-schedule the clinic visits.

Data of patients who discontinue or withdraw prior to allocation will be entered in the trial database and will be listed. Data of patients who discontinue or withdraw after allocation must be documented with the reason for withdrawal in source document and must be recorded in the electronic case report form (eCRF). The data must be included in the trial database and must be reported.

See [Section 6.2.4](#) for procedures to be followed for patients prematurely terminating the trial.

Pregnancy

If a patient becomes pregnant during the trial the investigational product needs to be stopped and the patient should be followed up until birth or until termination of the pregnancy. The data of the patient will be collected and reported in the CTR until patient's last visit and any events thereafter will be reported in the BI drug safety database. See [Section 5.3.7](#) for detailed information on event reporting in case of pregnancy.

3.3.4.2 Discontinuation of the trial by the sponsor

Boehringer Ingelheim reserves the right to discontinue the trial overall or at a particular trial site at any time for the following reasons:

1. Failure to meet expected enrolment goals overall or at a particular trial site
2. Emergence of any efficacy/safety information invalidating the earlier positive benefit-risk-assessment that could significantly affect the continuation of the trial
3. Violation of GCP, the CTP, or the contract disturbing the appropriate conduct of the trial

The Investigator / the trial site will be reimbursed for reasonable expenses incurred in case of trial termination (except in case of the third reason).

